3.2.1 Safety of Pfs230D1M-EPA/AS01 in Healthy Adults

Pilot Phase

In the pilot phase of the study, there was a staggered dose escalation of Pfs230D1M and Pfs25M, given individually and in combination. In the Pfs230D1M arms alone, vaccinations with the low dose of Pfs230D1M (13 μ g) and high dose of Pfs230D1M (40 μ g) were overall well-tolerated. Most of the related AEs were mild (Grade 1; 13 μ g: 23/29, 79%; 40 μ g: 42/51, 82%), with the majority being injection site pain. Laboratory abnormalities were also observed, with the majority being transient, asymptomatic Grade 1 (mild) and Grade 2 (moderate) neutropenias. As the high dose (40 μ g) of the Pfs230D1M/AS01 was determined safe and tolerable in the pilot study, it was selected to be used for the main phase of the study.

Main Phase

In the main phase of the trial, there was a full-dose arm (n=56) and a fractional-dose arm (n=61). The full-dose arm received Pfs230D1M-EPA/AS01 at 40 μg at 0, 1, 6, and 18 months. The fractional-dose arm received Pfs230D1M-EPA/AS01 at 40 μg at 0, 1, and 18 months and received a fractional dose of 8 μg of Pfs230D1M-EPA/AS01 at dose #3 at 6 months. Because there is no fractional dosing in the proposed trial, full details of the fractional dosing arm are not provided here; overall, the AE profile was similar to that of the full-dose arm, and further details can be found in the Investigator Brochure.

First 3 vaccinations: In the full-dose arm (n=56), the first three vaccinations were well tolerated with 66% (252/383) of the total AEs being mild. The most common Grade 1 AEs were injection site pain (95/252; 38%) followed by headache and malaria. Of the related Grade 2 AEs, 16/24 (67%) were injection site pain. Other related Grade 2 AEs were 2 episodes each of fever, headache, arthralgias, and neutropenia. Grade 1 injection site pain was reported in the full-dose arm in 95/168 (57%) doses, fractional-dose arm in 78/180 (43%) doses and control arm in 39/360 (11%) doses. Grade 2 injection site pain was also significantly greater in the full-dose and fractional-dose arms compared to the control. Grade 1 headaches were significantly greater in the full-dose arm than the control arm.

Booster dose: The fourth dose of Pfs230D1M-EPA/AS01 was well tolerated; most AEs were mild (Grade 1 AEs; 160/363, 44%). The most commonly reported Grade 1 AE was injection site

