5.1 Study Endpoints

Primary Endpoint:

• Incidence of local and systemic AEs and SAEs

Secondary Endpoints:

- Anti-Pfs230D1 IgG levels as measured by ELISA
- TRA/TBA of induced antibody in SMFA

Exploratory Endpoints:

- Cellular immune responses and antibody repertoire of functional antibody responses to vaccination
- RNA transcriptome quantification as detected by RNA sequencing comparing vaccinees to controls
- Host factors including but not limited to hemoglobinopathies, immune signatures, coinfections, and environmental, demographic, and socioeconomic characteristics

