5.2 Sample Size and Estimated Duration of Study

A total of 80 subjects will be vaccinated with either Pfs230D1-EPA/Matrix-M (n=60) or the rabies vaccine comparator (n=20). The last study visit will occur at Month 14 (12 months after the final immunization). Up to 150 subjects will be screened to accommodate possible screening failures.

The sample size was derived to be able to demonstrate safety, tolerability, and immunogenicity of the study vaccine as described in Section 14.1.

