14.1 Sample Size

Safety:

The arms are sufficiently sized for safety. For each dose level (n=20) in Arms 1a combined with 2a, and 1b combined with 2b, 1c combined with 2c, and 1d combined with 2d, vaccination of 20 subjects gives a power of at least **0.80** for detecting 1 or more serious or severe AEs that occur with a probability of **0.077** or more per subject (or **0.90** for an event with a probability of **0.109**).

If we combine all treated groups (arms 1a/2a, 1b/2b, 1c/2c), with a total of 60 subjects, we have **80% power** to detect 1 or more serious or severe AEs that occur with a probability of **0.026** or more per subject (or **0.90** for an event with a probability of .037).

The aforementioned calculations do not assume any historical data; they are statistical consequences of the binomial distribution.

We will compare all AE event proportions between the control arm and treated arm by Fisher's exact test.

Immunogenicity:

We plan to do a test for an overall signal with a global analysis. That is, we will combine arms 1a/2a, 1b/2b, and 1c/2c into an "any vaccination" group of n=60 and combine arms 1d and 2d into a "control" group of n=20. Using historical data from the AS01 trial, we are well powered to detect a log difference (>99.9% power) and ½ log difference (99.7% power).

Following this global test, testing specific arms is of interest. To adjust for multiplicity, we use Bonferroni corrected alpha of 0.05/3. To investigate the specific arms we conduct three tests: arms 1a/2a vs controls, arms 1b/2b vs controls, and arms 1c/2c vs controls. The controls use arms 1d and 2d. This makes each analysis n=20 vs n=20. As such, we are well powered to detect a log difference (>99.9% power) and ½ log difference (89.2% power).

These calculations were made assuming normal distributions with mean and standard deviations from the AS01 trial. 1000 simulations were run to see how often a significant result came from a Wilcoxon-Mann-Whitney test (WMW).

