14.2 Primary Objective

To assess safety and reactogenicity of administration of Pfs230D1-EPA/Matrix-M (all Arms):

- The frequency of systemic and local AEs will be summarized.
- A line listing of each clinical and laboratory AE classified as local, solicited, or other will be displayed in tables stratified by vaccine allocation.

- AEs will be summarized by severity and relationship to vaccine.
- The proportion of subjects with at least 1 AE will be compared by study group, and tests will be performed to assess whether these groups differ with respect to these proportions. To evaluate the difference in AEs between the initial vaccination and the subsequent vaccinations, a Wilcoxon signed-rank test (WSRT) will be performed, where the response for each subject is the difference between the numbers of AEs in the 7 days following each vaccination. To compare number and severity of AEs between control and vaccine arms, the Wilcoxon-Mann-Whitney test (WMW, also known as Wilcoxon rank sum test and Mann-Whitney U test) as well as linear regression may be used.
- SAEs occurring within the study period will be listed by relationship to vaccine.

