14.3 Secondary Objectives

14.3.1 ELISA Analysis

There are several questions of interest related to antibody response, which include the change in ELISA values from baseline after a given number of doses of vaccine and the change in ELISA values between doses. To address these questions, we will use an arm-specific WSRT within the 20 subjects receiving a given vaccine dose.

The data from subjects who had Pfs230 ELISA measurements after receiving two doses on protocol #17-I-N006 (Pfs230/AS01 trial) allow us to estimate the SD of the log transformed Pfs230 ELISA responses at baseline (mean 3.688401 SD 0.5490291) and 3 months post vaccination 2 (mean 5.356736 SD 0.8868963).

Assuming similar values in this trial, there would be over 0.99 power to detect the difference between baseline and 3 months post vaccination 2. This approximate power is calculated counting the number of significant comparisons out of a thousand comparisons between random normal draws from N(3.68,0.55) and N(5.36, 0.88) using the Wilcoxon test.

Using the background information from protocol #17-I-N006, we have greater than 80% power to reject a 2-sided 0.05 level WMW test if the geometric mean Pfs230 ELISA baseline level was 2.3-fold higher geometric mean than the level of detection in the vaccinated group post vaccination 2. (Note: 2.3-fold is lower than the 5.31-fold observed in protocol #17-I-N006, so we treat these numbers as conservative.) This approximate power is calculated counting the number of significant comparisons out of a thousand comparisons between random normal draws from N(3.68,0.55) and N(3.68+log(2.3), 0.88) using the Wilcoxon test.

ELISA results will be analyzed by Wilcoxon-Mann-Whitney test, as the simulated power calculations were conducted.

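### Fisher's exact test for AE proportions is valid but conservative at these arm sizes; Boschloo's exact test recovers up to about 12 points of power at 20 v 20 and about 12 to 13 at 60 v 20 near a 5% control rate

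*Combined protocol and SAP*

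**What the plan says.** The primary endpoint in Section 5.1 is "Incidence of local and systemic AEs and SAEs". The only test named for AE proportions is in Section 14.1, under the safety sample size: "We will compare all AE event proportions between the control arm and treated arm by Fisher's exact test". Section 14.2 returns to the comparison without naming a test: "The proportion of subjects with at least 1 AE will be compared by study group".

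For these AE tests the plan gives no alpha, sidedness, multiplicity rule or power. A two-sided 0.05 level appears only in an ELISA power statement in Section 14.3.1 ("we have greater than 80% power to reject a 2-sided 0.05 level WMW test"). The multiplicity rule in Section 14.1 ("To adjust for multiplicity, we use Bonferroni corrected alpha of 0.05/3") belongs to the dose-specific immunogenicity tests. The safety sizing rests on the chance of seeing at least one serious or severe AE, not on a comparison between arms.

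Section 5.2 gives 60 vaccinees and 20 controls. The dose-level size is written out for immunogenicity ("This makes each analysis n=20 vs n=20"), and the same arms supply the AE data.

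**The concern.** Fisher's test conditions on the total number of affected participants. In small samples the conditional distribution has few attainable p-values, so the true error rate falls well short of the nominal level. In an efficacy test that caution protects participants. In a safety comparison it works the other way, because real excesses of reactogenicity over rabies vaccine are more often left non-significant.

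An unconditional exact test on the same table can use more of the permitted 5% without exceeding it. At stake is sensitivity to common and moderately common AEs in a first-in-human trial. Section 1.2 makes a later combination trial depend on this vaccine being shown safe and well tolerated.

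**Working it through.** **Inputs.** Arm sizes 20 v 20 and 60 v 20 (Sections 5.2 and 14.1). Two-sided 0.05 for AEs is an assumption. Section 3.2.1 supplies illustrative rates from the AS01 trial: "Grade 1 injection site pain was reported in the full-dose arm in 95/168 (57%) doses", against 11% (39/360) of control doses. These are per dose; using them per participant is a second assumption. All other rate pairs are illustrative.

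**1. The plan's own safety figures.** Chance of at least one event = 1 − (1 − p)^n.
- n = 20: 1 − 0.923^20 = 0.799; 1 − 0.891^20 = 0.901.
- n = 60: 1 − 0.974^60 = 0.794; 1 − 0.963^60 = 0.896.

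The stated 0.80 and 0.90 reproduce to within rounding.

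**2. True size of Fisher's test.** List every outcome (x, y) and mark those with two-sided Fisher p ≤ 0.05. Then size(p) = Σ Bin(x; n1, p) · Bin(y; n2, p) over the marked outcomes, maximised over the common rate p.
- 20 v 20: maximum 2.53% (1.2% at a 10% event rate, 0.2% at 5%).
- 60 v 20: maximum 3.62% (2.4% at 10%, 1.9% at 5%).

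**3. Boschloo's test.** Take the two-sided Fisher p-value as the test statistic and raise its cut-off as far as the maximum size stays at or below 5%.
- 20 v 20: cut-off 0.0915, maximum size 4.64%.
- 60 v 20: cut-off 0.0636, maximum size 4.86%.

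Both cut-offs exceed 0.05, so every table that Fisher rejects is also rejected here.

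**4. A table that changes: 8/20 v 2/20.** The Fisher p-value is 2 × [C(20,8)·C(20,2) + C(20,9)·C(20,1) + C(20,10)] / C(40,10) = 2 × (23,934,300 + 3,359,200 + 184,756) / 847,660,528 = 0.065. That is non-significant by Fisher and significant by Boschloo (0.065 < 0.0915). The same holds for 6 v 1 (0.091) and 9 v 3 (0.082), and at 60 v 20 for 10/60 v 0/20 and 11/60 v 0/20.

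**5. Power.** This is the same sum with the two arms' own rates.

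| Arms | Vaccine v control rate | Fisher | Boschloo |
|---|---|---|---|
| 20 v 20 | 37% v 9% (largest gain, 1% grid) | 45.3% | 57.1% |
| 20 v 20 | 40% v 10% | 49% | 61% |
| 20 v 20 | 30% v 5% | 45% | 54% |
| 20 v 20 | 50% v 10% | 74% | 82% |
| 20 v 20 | 57% v 11% | 84.7% | 89.5% |
| 20 v 20 | 10.9% v 0 | 5.9% | 5.9% |
| 60 v 20 | 17% v 0 | 31.7% | 58.1% |
| 60 v 20 | 21% v 5% | 27% | 40% |
| 60 v 20 | 25% v 5% | 44.4% | 56.8% |
| 60 v 20 | 30% v 5% | 66% | 74% |
| 60 v 20 | 75% v 40% | 76% | 81% |
| 60 v 20 | 50% v 20% | 65.0% | 66.1% |
| 60 v 20 | 57% v 11% | 97.6% | 97.7% |

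At 60 v 20 with a control rate between 10% and 50%, the largest gain is 7.7 points.

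**6. The price in false signals.** Three dose arms share one control group and have no multiplicity rule. For one AE with common rate p, the chance of any false positive is Σ_y Bin(y; 20, p) · [1 − (1 − q_y)^3], where q_y is the chance that a dose arm is declared different given y affected controls. At p = 20% it rises from 5.9% (Fisher) to 11.2% (Boschloo), and at 30% from 6.5% to 11.3%.

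**The case against.** The strongest reply is that nothing in the plan is wrong. Fisher's test is valid at these sizes, the plan claims no power for it, and the safety figures it does state reproduce. That stands, and it limits the point to efficiency.

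No trial decision turns on this p-value either. The halting rules in Section 12.9 are mainly event counts, and Section 14.2 is largely descriptive, with rank tests and regression allowed for number and severity of AEs. A reader might infer that a non-significant Fisher result would be reported as showing the vaccine to be no more reactogenic than rabies vaccine. The documents say no such thing. They show only that real differences would be flagged less often.

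The gains also depend on the event. At the only pair of rates taken from the documents (57% v 11%), the gain is 4.8 points at 20 v 20 and about nil at 60 v 20. At 20 v 20, the serious or severe AE rates used for sizing (7.7% and 10.9%), set against none in controls, gain nothing. The singular wording in Section 14.1 could mean only the pooled comparison, so the 20 v 20 AE test is a reading of the plan rather than its explicit statement.

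Finally, a reader might take the switch to be free. It is not: the 5% guarantee is per test, and step 6 shows the extra false signals. Nor is every packaged routine suitable. For 59/60 v 17/20, Fisher gives p = 0.046, while SciPy's two-sided Boschloo gives 0.061 because it uses a different rule. These limits shape the change but do not remove the case for it.

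**Conclusion.** The point holds as a loss of efficiency in the primary safety comparison, not as an error in a stated figure. At two-sided 0.05, Fisher's test uses at most about half of the permitted error at 20 v 20 and under three-quarters at 60 v 20. Boschloo's test never has less power at these sizes and holds each test at or below 5%.

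No single figure describes the gain. It reaches 11.8 points at 20 v 20. At 60 v 20 it is 12 to 13 points near a 5% control rate, more as the control rate approaches zero, and at most 7.7 points for control rates of 10% to 50%. The benefit lies with moderately common AEs; it is small or absent for very common pain at 60 v 20 and for rare events at 20 v 20.

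The conclusion assumes two-sided 0.05 and full arm sizes. The 57% v 11% example also treats per-dose rates as per-participant rates.

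**What to change.** In Sections 14.1 and 14.2:

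- Name Boschloo's exact unconditional test, ordered by the two-sided Fisher p-value, at two-sided 0.05, for participant-level AE proportions.
- State the comparisons: pooled vaccine v control (60 v 20) and each dose v control (20 v 20).
- Keep Fisher p-values as a secondary column.
- Specify the ordering in the analysis code rather than relying on a package default, and recompute the cut-off if the analysed numbers differ from 20 or 60.
- Say that AE p-values are unadjusted and serve as screening.

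The cost is wording and a short piece of code, with no added participants, visits or data. The downsides are a less familiar test and more unadjusted false-positive signals: about 6% to 11% across three dose comparisons of one AE at a 20% to 30% rate. That is tolerable for safety screening.

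### Single-step Bonferroni for the three dose-versus-control ELISA tests is valid, but Holm's step-down on the same p-values keeps the 5% familywise error and can only reject as many or more

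*Combined protocol and SAP*

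**What the plan says.** Section 14.1 (Immunogenicity) starts with a pooled comparison of 60 vaccinees with 20 rabies controls: "We plan to do a test for an overall signal with a global analysis". It then moves to the doses: "Following this global test, testing specific arms is of interest". The comparisons are "arms 1a/2a vs controls, arms 1b/2b vs controls, and arms 1c/2c vs controls", with one shared control group ("The controls use arms 1d and 2d") and equal sizes ("This makes each analysis n=20 vs n=20"). The adjustment is "To adjust for multiplicity, we use Bonferroni corrected alpha of 0.05/3".

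For a half-log difference the stated power is 99.7% for the pooled test and 89.2% per arm; for a full log both exceed 99.9%. The test is the Wilcoxon-Mann-Whitney (WMW) test, with power from 1000 simulated normal data sets.

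Neither 14.1 nor 14.3.1 mentions a step-down or closed procedure. Section 14.1 gives no alpha for the pooled test and does not say whether a non-significant pooled result stops the arm tests.

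**The concern.** Single-step Bonferroni holds every comparison to 0.05/3 even after another has been rejected. Once one null hypothesis is rejected, at most two can still be true, so 0.05/2 suffices for the next, and 0.05 for the last. Keeping 0.05/3 throughout gives power away without any gain in error control.

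The arm-level answers matter here. Section 1.2 gives antigen dose-sparing as the reason for the 20 µg arm. The low-dose arm has both the least antigen and half the adjuvant (section 1.2.1). A weaker dose is the one that a fixed threshold penalises most.

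**Working it through.** **Inputs.** Three vaccine arms of 20 and one shared control of 20 (14.1). Per-arm alpha 0.05/3 = 0.0167 (14.1). SDs 0.549 at baseline and 0.887 at 3 months after vaccination 2, from the AS01 trial (14.3.1), used for control and vaccine arms. Two-sided testing (stated in 14.3.1, not in 14.1). Log base: 5.3567 − 3.6884 = 1.668 and exp(1.668) = 5.30, against the plan's 5.31-fold, so the logs are natural. Half a log10 is then ln(10)/2 = 1.151. Assumed, because the documents do not say: pooled-test alpha 0.05 and no dropout.

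**Reproducing the plan's figure.** Simulated per-arm WMW power at 0.05/3:
- SDs 0.549/0.887, shift 1.151: about 98%
- SD 0.887 in both groups, shift 1.151: about 92%
- SDs 0.549/0.887, shift 0.5: about 33%

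None gives 89.2%. The Monte Carlo error of the plan's figure is √(0.892 × 0.108/1000) ≈ 1 point. A common SD near 0.93, or the printed SDs scaled up by about 1.25, would come close. Section 14.1 does not print the SDs it used, so 89.2% is taken as given and the gain is also shown for other effects.

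**Error control.** Holm compares the ordered p-values with 0.05/3, 0.05/2 and 0.05, stopping at the first failure. If m of the three nulls are true, the first true null to be rejected meets a threshold of at most 0.05/m. A false rejection therefore needs the smallest of m true-null p-values to be at most 0.05/m, which has probability at most m × 0.05/m = 0.05. Independence is not used, so the shared control does no harm. Simulated familywise error was 3.9%, 4.1% and 5.0% with three, two and one true nulls. Each Holm threshold is at least 0.05/3, so everything Bonferroni rejects, Holm rejects.

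**Size of the gain** (simulated two-sided WMW, three equally effective doses):

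| Scenario | All three, Bonferroni | All three, Holm |
|---|---|---|
| Shift 0.92, SDs 0.549/0.887 (set to give about 89% per arm) | 73% | 88% |
| 2.3-fold, shift ln(2.3) = 0.83, SDs 0.55/0.88 (14.3.1) | 59% | 79% |
| Half log10, shift 1.151, SDs 0.549/0.887 | 95% | 99% |
| AS01 effect (1.668), or a full log10 | about 100% | about 100% |

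Per-arm power goes from about 89% to 95% in the first row and from about 82% to 90% in the second.

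**Normal-theory check of the first row.** The noncentrality is 2.394 + 1.237 = 3.631, the sum of the critical value at 0.05/3 and the normal quantile of 0.892. The correlation from the shared control is 0.549²/(0.549² + 0.887²) = 0.277. All-three power is then 73.8% with Bonferroni and 87.0% with Holm.

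**One weaker dose.** With shifts 0.92, 0.92 and 0.46, power for the weak arm goes from about 28% to 45%.

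**What gating would do.** The alternative is a closed procedure that uses the pooled test at 0.05 as its first step. Power for each fully active dose:

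| Shifts in the three doses | Bonferroni | Gated closed procedure |
|---|---|---|
| 0.92, 0, 0 | 89% | 24% |
| 0.92, 0.92, 0 | 89% | 83% |

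Inactive doses dilute the pooled group. Ungated Holm stays at or above Bonferroni in both rows.

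**The case against.** The strongest reply is that nothing is wrong with the plan. Bonferroni is prespecified and valid, the primary endpoint is safety, ELISA is secondary, and confirming all three doses is nowhere a stated goal. All of that stands. It limits this to an efficiency point, for which the per-arm gain is the fairer summary.

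The gain is also conditional. The 0.92 shift (exp(0.92) ≈ 2.5-fold) was solved to match 89.2% and is not an effect the plan names. A reader might take 73% to 88% as a general improvement. The documents do not support that: with the printed SDs at half a log10 the gain is 3 to 4 points, and at the effect seen in the AS01 trial it is nil.

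Two stronger readings should be resisted.
- A reader might infer that, because a pooled test already comes first, building it in as a gate is free. It is not, as the last table shows.
- A reader might infer that the plan spends more than 5%. If the pooled test is run at 0.05 and all four tests count as claims, the chance of any false positive under the complete null is about 6.5%. But the pooled alpha is not stated, and "Following this global test, testing specific arms is of interest" can equally be read as sequential. This is an ambiguity, not a demonstrated inflation. Ungated Holm would not remove it, since under the complete null Holm and Bonferroni have the same chance of any rejection.

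**Conclusion.** The point holds as a minor, free improvement. Ungated Holm dominates single-step Bonferroni at the same 5% familywise error, and that conclusion needs no assumption about effect size, SD or correlation.

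The size does need assumptions. With three equal effects at about the stated 89.2% power, per-arm power rises by about 6 points and all-three power by about 15. The all-three gain is about 20 points at the 2.3-fold scenario, about 4 at half a log10 with the printed SDs, and zero at a full log. These figures assume normal log titres, two-sided tests and no dropout. The plan's procedure is not an error. That 89.2% cannot be rebuilt from the printed SDs does not show it to be wrong, because 14.1 may rest on AS01 values that are not printed.

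**What to change.** In section 14.1, replace the Bonferroni sentence with: *The three dose-versus-control p-values are judged by Holm's step-down procedure at two-sided familywise 0.05, and Holm-adjusted p-values are reported.*

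Add a sentence stating the pooled test's alpha and labelling it a separate test for an overall signal, outside the arm-level claims and not a condition for them. Print the means and SDs behind the 89.2%.

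The cost is a few lines of text, settled before unblinding. Participants, samples and visits do not change. The stated per-arm power at 0.05/3 can stay, as a lower bound for power under Holm.
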